1.2 OBJECTIVES

1.2.1 Primary objectives

The primary objectives of the LTS13769 study are to assess the long-term safety and pharmacokinetics (PK) of avalglucosidase alfa in patients with Pompe disease who have previously completed an avalglucosidase alfa study.

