1.6 STATISTICAL MODIFICATIONS MADE IN THE STATISTICAL ANALYSIS PLAN

The following main modifications have been made in this version of SAP:

- Added Global Lung Initiative (GLI) 2012 reference equations to calculate FVC % predicted values
- Updated immunogenicity analysis. Some revisions of immunogenicity analysis are made to be consistent with integrated immunogenicity analysis plan.
- Added the second equations for calculating reference value for percentage of predicted total distance walked in 6MWT
- Added Algorithm-defined IARs to be consistent with integrated safety analysis plan
- Updated drug compliance definition to be consistent with COMET and mini-COMET studies
- Added K-M analysis for treatment-emergent adverse events
- The Appendix on Potentially Clinically Significant Abnormalities Criteria was updated

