2.1.4 Safety endpoints

The safety analysis will be based on the reported adverse events (AEs) and other safety information, such as clinical laboratory data, vital signs, ECG, etc.

Observation period

The observation period will be divided into the following epochs:

- The screening epoch is defined as the study period preceding treatment, starting from the signed informed consent date (TDR12857) up to the first administration of IMP. (Note: medications known to have been taken by the patients within 28 days of the TDR12857 screening/baseline visit will be recorded in the CRF as well.)
- The treatment epoch is defined as the time from the start of the first administration of the IMP in the TDR12857 through the completion of the last administration of the IMP.
 - Before- and after-rebaseline periods within the treatment epoch will be used for select analyses
- The residual treatment epoch is defined as the time subsequent to the treatment epoch, from the completion of the last administration of the IMP through the last administration of the IMP + 28 days or the end of the protocol-defined follow-up period, whichever is earlier.

The treatment-emergent adverse event (TEAE) period will include both treatment and residual treatment epochs.

- The **posttreatment** epoch is defined as the period of time starting the day after the end of the treatment-emergent adverse event period up through the end of the study.

The on-study observation period is defined as the time from start of treatment in the TDR12857 until the end of the LTS13769 study (defined as the last follow-up visit as defined in LTS13769 protocol Section 10.1.2.9).

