2.4.5.1 Analyses of adverse events

Generalities

The primary focus of adverse event reporting will be on treatment-emergent adverse events. Pretreatment and posttreatment adverse events will be described separately.

If an adverse event date/time of onset (occurrence, worsening, or becoming serious) is incomplete, an imputation algorithm will be used to classify the adverse event as pretreatment, treatment-emergent, or posttreatment. The algorithm for imputing date/time of onset will be conservative and will classify an adverse event as treatment-emergent unless there is definitive information to determine it is pretreatment or posttreatment. Details on classification of adverse events with missing or partial onset dates are provided in [Section 2.5.3](#).

Adverse event incidence tables will present adverse events grouped by SOC and PT, including the number and percentage of patients experiencing AEs in each SOC/PT category and the associated event counts (see the paragraph below for sorting order). Multiple occurrences of the same event in the same patient will be counted only once in the tables within observation period presented

(pretreatment, treatment-emergent, and posttreatment). The denominator for computation of percentages is the safety population within each patient and dose group.

Sorting within tables ensures the same presentation for the set of all adverse events within the observation period (pretreatment, treatment-emergent, and posttreatment). For that purpose, the table of all treatment-emergent adverse events presented by SOC and PT sorted by the internationally agreed SOC order and decreasing frequency of PTs within SOCs will define the presentation order for all other tables unless otherwise specified. Sorting according to frequency of PTs will be based on the sum of patient counts for the patients in the 20mg/kg dose groups. In the case of the AE by maximal severity tables, the sum of patient counts for the severe AEs from patients in the 20 mg/kg dose groups will be used for the sorting of PTs.

For patients previously assigned to the 5 or 10 mg/kg dose groups in the TDR12857, entered the LTS13769 study, and switched to the 20 mg/kg dose group (LTS-switch group), additional AE summaries, as indicated in respective subsections below, will be generated for comparison of before- and after-rebaseline adverse events in these patients.

Analysis of all treatment-emergent adverse events

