The following treatment-emergent adverse event summaries will be generated for the safety population.

- Overview of treatment-emergent adverse events, summarizing number and percentage of patients and number of events with any
 - Treatment-emergent adverse event(s)
 - Severe treatment-emergent adverse event(s)
 - Serious treatment-emergent adverse event(s)
 - Treatment-emergent AESI(s)
 - IARs (protocol- and algorithm-defined)
 - Treatment-emergent adverse event(s) leading to permanent treatment discontinuation
 - Treatment-emergent adverse event leading to death
- All treatment-emergent adverse events by primary SOC, HLT, and PT, showing number (%) of patients with at least 1 treatment-emergent adverse event and number of events sorted by the SOC internationally agreed order. The other levels (HLT, and PT) will be presented in alphabetical order.
- All treatment-emergent adverse events by primary SOC and PT, showing the number (%) of patients with at least 1 treatment-emergent adverse event and number of events, sorted by the internationally agreed SOC order and by decreasing incidence of PTs within each SOC. This sorting order will be applied to all other tables, unless otherwise specified.
 - Additional summaries of before- and after-rebaseline periods will be presented for the LTS-switch group
- All treatment-emergent adverse events by PT, showing the number (%) of patients with at least 1 treatment-emergent adverse event and number of events, sorted by decreasing incidence of PTs.

- All treatment-emergent adverse events regardless of relationship and related by primary SOC and PT, showing the number (%) of patients with at least 1 treatment-emergent adverse event and number of events, sorted by the internationally agreed SOC order. The PT levels will be presented in alphabetical order.
 - Additional summaries of before- and after-rebaseline periods will be presented for the LTS-switch group
- All treatment-emergent adverse events by maximal severity, presented by primary SOC and PT, showing the number (%) of patients with at least 1 treatment-emergent adverse event and number of events by severity (ie, mild, moderate, or severe), sorted by the internationally agreed SOC order and by decreasing incidence of PTs within each SOC.
 - Additional summaries of before- and after-rebaseline periods will be presented for the LTS-switch group
- A by-patient listing of AEs, ADA, and IgE, sorted chronologically, will be presented.

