A listing of potential immune mediated reactions will be provided. All treatment-emergent adverse events, by standardized MedDRA query (SMQ) and PT, showing the number (%) of patients and number of events with at least 1 PT, sorted by decreasing incidence of PTs within each SMQ.

Analysis of adverse events with AESIs

- Treatment-emergent AESIs by Primary SOC and PT, showing the number (%) of patients and number of events, sorted by the internationally agreed SOC order and by decreasing incidence of PTs within each SOC.
- All treatment-emergent AESIs by maximal severity, presented by primary SOC and PT, showing the number (%) of patients with at least 1 treatment-emergent adverse event and number of events by severity (ie, mild, moderate, or severe), sorted by the internationally agreed SOC order and by decreasing incidence of PTs within each SOC.
- Summary tables of infusion associated reactions (IARs) as defined by the 2 definitions will be presented by Primary SOC and PT for each patient group and dose level.
- All IARs by maximal severity, presented by primary SOC and PT, showing the number (%) of patients with at least 1 treatment-emergent adverse event and number of events by severity (ie, mild, moderate, or severe), sorted by the internationally agreed SOC order and by decreasing incidence of PTs within each SOC.
- A detailed listing of patients who experience IARs including information on severity, seriousness, relationship to IMP, timing from first infusion to the onset of the IAR, IAR definition(s) met, action taken regarding study treatment, other action taken, and patient outcome, will be provided.

Severe cutaneous and immune-mediated reactions

- Treatment-emergent severe cutaneous and immune-mediated reactions by Primary SOC and PT, showing the number (%) of patients and number of events, sorted by the internationally agreed SOC order and by decreasing incidence of PTs within each SOC.

Analysis of pretreatment and posttreatment adverse events

- All pretreatment adverse events will be presented in a patient listing.
- All posttreatment adverse events will be presented in a patient listing.

Kaplan-Meier estimates

- A summary table of Kaplan-Meier estimates of TEAEs by 6-month time intervals will be provided.

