Month 27 in LTS (1004)	Week 143	960 to 1050 days
Month 30 in LTS (1095)	Week 156	1051 to 1141 days
Month 33 in LTS (1186)	Week 169	1142 to 1232 days

VISIT (target study day*)	Analysis Visit	Analysis Visit Window (in study days*)
Month 36 in LTS (1277)	Week 182	1233 to 1324 days
Month 39 in LTS (1369)	Week 195	1325 to 1415 days
Month 42 in LTS (1460)	Week 208	1416 to 1506 days
Month 45 in LTS (1551)	Week 221	1507 to 1597 days
Month 48 in LTS (1642)	Week 234	1598 to 1689 days
Month 51 in LTS (1734)	Week 247	1690 to 1780 days
Month 54 in LTS (1825)	Week 260	1781 to 1871 days
Month 57 in LTS (1916)	Week 273	1872 to 1962 days
Month 60 in LTS (2007)	Week 286	1963 to 2054 days
Month 63 in LTS (2099)	Week 299	2055 to 2145 days
Month 66 in LTS (2190)	Week 312	2146 to 2236 days
Month 69 in LTS (2281)	Week 325	2237 to 2327 days
Month 72 in LTS (2372)	Week 338	2328 to 2402 days

*Study days are days since the first infusion in the TDR12857 study.

**For patients who enrolled in LTS13769, the upper boundary of the window is 273 days or (1st day of LTS – 1), whichever is earlier; for patients who didn't enroll in LTS13769, use study day 273 as cutoff.

Table 4 – Biochemistry

VISIT (target study day*)	Analysis Visit	Analysis Visit Window (in study days*)
Baseline	Baseline	
Week 1 in TDR (1)	Week 1	1 to 8 days
Week 3 in TDR (15)	Week 3	9 to 21 days
Week 5 in TDR (29)	Week 5	22 to 35 days
Week 7 in TDR (43)	Week 7	36 to 49 days
Week 9 in TDR (57)	Week 9	50 to 63 days
Week 11 in TDR (71)	Week 11	64 to 77 days
Week 13 in TDR (85)	Week 13	78 to 91 days
Week 15 in TDR (99)	Week 15	92 to 105 days
Week 17 in TDR (113)	Week 17	106 to 119 days
Week 19 in TDR (127)	Week 19	120 to 133 days
Week 21 in TDR (142)	Week 21	134 to 148 days
Week 23 in TDR (156)	Week 23	149 to 162 days
Week 25 in TDR (169)	Week 25	163 to 176 days/(1 st day of LTS – 1)**
Day 1/Week 0 in LTS (183)	Week 28	(1 st day of LTS) to 198 days
Month 1 in LTS (213)	Week 32	199 to 228 days
Month 2 in LTS (244)	Week 36	229 to 259 days
Month 3 in LTS (274)	Week 40	260 to 289 days
Month 4 in LTS (304)	Week 44	290 to 319 days
Month 5 in LTS (335)	Week 48	320 to 350 days
Month 6 in LTS (365)	Week 52	351 to 380 days
Month 7 in LTS (396)	Week 56	381 to 411 days
Month 8 in LTS (426)	Week 61	412 to 441 days

VISIT (target study day*)	Analysis Visit	Analysis Visit Window (in study days*)
Month 9 in LTS (456)	Week 65	442 to 471 days
Month 10 in LTS (487)	Week 69	472 to 502 days
Month 11 in LTS (517)	Week 74	503 to 532 days

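### No adverse event summary covering all patients gives rates by treatment interval or per patient-year, and the Kaplan-Meier table, which uses first events only, cannot fill that gap

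*SAP*

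**What the plan says.** The SAP's primary objectives (1.2.1) are "to assess the long-term safety and pharmacokinetics (PK) of avalglucosidase alfa in patients with Pompe disease" who have completed an earlier study of the drug. Protocol 6.2.1 sets an initial 6 years per patient, followed by a further phase.

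SAP 2.1.4 runs the treatment epoch "from the start of the first administration of the IMP in the TDR12857 through the completion of the last administration of the IMP", and adds: "The treatment-emergent adverse event (TEAE) period will include both treatment and residual treatment epochs". TEAEs are therefore gathered over one long block that begins in the parent study.

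Within that block, the SAP 2.4.5.1 tables give patients with an event, percentages and event counts. The denominator is the safety population in each patient and dose group. On repeats the SAP says: "Multiple occurrences of the same event in the same patient will be counted only once in the tables within observation period presented". Protocol 11.5.3 tabulates by dosing, severity and relationship, with no time dimension.

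Four TEAE outputs do involve time:

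- **Kaplan-Meier table, SAP 2.4.5.1.** "A summary table of Kaplan-Meier estimates of TEAEs by 6-month time intervals will be provided". SAP 1.6 lists it among the changes in this version: "Added K-M analysis for treatment-emergent adverse events". Event category, time origin, censoring rule and grouping are not given.
- **Re-baseline split, SAP 2.4.5.1.** For TEAE and serious TEAE tables: "Additional summaries of before- and after-rebaseline periods will be presented for the LTS-switch group". It is not specified for the IAR tables.
- **Chronological by-patient listing** of adverse events, anti-drug antibodies and IgE.
- **IAR listing** that includes time from first infusion.

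Exposure is summarised (SAP 2.4.3.1; protocol 11.9 adds quarterly counts of patients still on treatment), but no adverse event rate uses it.

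**The concern.** An extension study of this length should be able to say whether adverse events become more common, less common or stay level as treatment continues. That needs events set against the patient-time in which they occurred, period by period. Pooled percentages and counts cannot supply it: a patient with ten events in year 1 and one with ten in year 5 contribute identically.

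The Kaplan-Meier table looks as if it answers the question because it is laid out in 6-month rows. It answers a different one, namely how long until a patient's first event. A patient who has had that event leaves the risk set and adds nothing to later rows. If the event is any TEAE and TEAEs are frequent, the later rows rest on few patients, and those are selected for having had none so far. A late rise in recurring events, IARs for example, could then go unseen in every summary that covers all patients.

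**Working it through.** **Inputs.** The documents give no TEAE rate, sample size or power figure, so there is no planned number to reproduce. The rate r (events per patient-year) is an assumption throughout, shown over a range. The TEAE clock starts at the first TDR12857 dose (SAP 2.1.4). Extension Day 1 has target study day 183, about 0.5 year (SAP Appendix B, biochemistry windows). The last target, Month 72, is study day 2372, and 2372/365.25 = 6.5 years.

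**Step 1: first-event curve at a constant rate.** F(t) = 1 − exp(−r·t).

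| r per patient-year | 0.5 y | 1 y | 2 y | 6 y |
|---|---|---|---|---|
| 0.25 | 12% | 22% | 39% | 78% |
| 0.5 | 22% | 39% | 63% | 95% |
| 1 | 39% | 63% | 86% | 99.8% |
| 2 | 63% | 86% | 98% | 100% |
| 4 | 86% | 98% | 100% | 100% |

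Reaching 90% by 6 months needs r = ln(10)/0.5 = 4.6; by 12 months, ln(10)/1 = 2.3. At r = 4, exp(−4 × 0.5) = 14% of patients would be free of a first event at extension entry.

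**Step 2: between-patient variation.** With gamma frailty of variance 1, F(t) = 1 − 1/(1 + r·t). At r = 4 this gives 67%, 80%, 89% and 96% at the same four times, so the curve rises more slowly.

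**Step 3: can the table detect a late change?** Let the rate be multiplied by m = 0.5, 1 or 2 after year 1. The cumulative rate at 6.5 years is H = r × 1 + r × m × 5.5. The estimate is 1 − exp(−H), or 1 − 1/(1 + H) with frailty. Events per patient over years 1 to 6.5 are r × m × 5.5.

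| Case | Halved | Same | Doubled |
|---|---|---|---|
| r = 4, H | 15 | 26 | 48 |
| r = 4, Kaplan-Meier at 6.5 y | 1.00 | 1.00 | 1.00 |
| r = 4 with frailty | 0.94 | 0.96 | 0.98 |
| r = 4, events per patient, years 1 to 6.5 | 11 | 22 | 44 |
| r = 1, Kaplan-Meier at 6.5 y | 0.977 | 0.999 | 1.00 |
| r = 0.25, H | 0.94 | 1.63 | 3.00 |
| r = 0.25, Kaplan-Meier at 6.5 y | 0.61 | 0.80 | 0.95 |

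For frequent events, a fourfold contrast in the late rate moves the estimate by at most 0.04, while event counts separate in full proportion. For infrequent events the estimate does respond, though repeat events are still ignored.

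**Step 4: precision of interval rates.** Assume 20 patients each followed for 1 year in both periods, with independent Poisson counts. The 95% interval for a year-6 to year-1 rate ratio is the estimate multiplied and divided by exp(1.96 × √(2/(20r))): 1.36 at r = 4 and 1.55 at r = 2. With 10 patients and r = 2 the factor is 1.86. Event clustering could change these widths.

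**The case against.** The strongest reply is that the plan has more on timing than this table.

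- A reader might infer that the Kaplan-Meier table is the only time-based TEAE analysis. It is not. For LTS-switch patients, TEAEs and serious TEAEs are split before and after re-baseline: overall, by relationship and by maximal severity. That stands. But the split covers one subgroup, its two periods also differ in dose, they may differ in length, and there is no patient-time denominator.
- The chronological listing and the IAR listing would let a careful reader notice a late cluster, and the data monitoring committee holds periodic safety reviews (protocol 6.3.1). That also stands, but listings and oversight are not a summary of whether events rise or fall.
- Repeat events are not lost altogether, because event counts accompany patient counts. They are pooled over the period, however, so their timing is lost.
- The SAP does not say that the Kaplan-Meier event is any first TEAE. Use of the first event follows from the method; the category is left open, and separate estimates for serious events or IARs are not excluded.
- Protocol 9.1.1 bases the safety profile on incidence, severity and the cumulative nature of TEAEs, the analysis is descriptive, and numbers are small. This limits what interval rates can show by subgroup, but it does not remove the need for them in a study of long-term safety.

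**Conclusion.** The gap is real. Neither SAP 2.4.5.1 nor protocol 11.5.3 plans a TEAE, serious TEAE or IAR rate per patient-year or by treatment interval for all patients, and a first-event estimate cannot stand in for one. For frequent events it is nearly blind to a late change in rate.

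The size is illustrative because every rate is assumed. Two stronger readings are tempting and are not supported:

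- **That the curve saturates in the first intervals and says nothing about later years.** No document gives a TEAE rate. Reaching 90% by 6 months needs about 4.6 events per patient-year, between-patient variation slows the rise, and infrequent categories would not saturate.
- **That follow-up is 6 to 8 years for everyone.** Protocol 6.2.1 caps it at 8 years only in the UK, Germany and Denmark; elsewhere the further phase runs until approval in the patient's country.

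This is a worthwhile, low-cost improvement to how the primary objective is reported. It does not invalidate the planned tables.

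**What to change.** Add to SAP 2.4.5.1, for TEAEs, serious TEAEs and IARs, one descriptive table by 6-month or yearly treatment interval. Pool it over all patients, and show it by patient and dose group where numbers allow. Each row gives:

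- patients on treatment;
- patient-years in the interval;
- patients with at least one event in the interval;
- all events, not only the first, per patient-year.

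Keep Kaplan-Meier for infrequent first events such as serious TEAEs and IARs, and state its event, time origin and censoring rule.

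The data are already collected, and the exposure summaries in SAP 2.4.3.1 and the quarterly on-treatment counts in protocol 11.9 are close to the denominators needed. No test is added, so no multiplicity question arises. The cost is a few extra tables and modest programming. The drawback is wide uncertainty in small subgroups, so the pooled rows should carry the interpretation.

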2.4.5.2 Deaths

The following summaries of deaths will be generated for the safety population.

- Number (%) of patients who died by study period (on-study, on-treatment, posttreatment, and poststudy) and, if captured, reasons for death Treatment-emergent adverse events leading to

death (death as an outcome on the adverse event CRF page as reported by the Investigator) by primary SOC and PT showing number (%) of patients and number of events sorted by internationally agreed SOC order, with PT presented in alphabetical order within each SOC.

2.4.5.3 Analyses of laboratory variables

The summary statistics (including number, mean, median, standard deviation, minimum, and maximum) of all laboratory variables (central laboratory values, changes from baseline, and changes from rebaseline [LTS-switch group only]) will be calculated for each applicable visit or study assessment (baseline, each postbaseline time point) by patient and dose group. For select laboratory assessments (alanine aminotransferase (ALT), aspartate aminotransferase (AST), creatinine, creatine kinase (CK), and creatine kinase MB band (CK-MB)), mean changes from baseline with the corresponding standard error will be plotted over time in each patient group and dose level. This section will be organized by biological function as specified in [Section 2.1.4.3](#).

The incidence of PCSAs (list provided in Appendix A) at any time during the treatment-emergent adverse event period will be summarized by biological function and treatment group according to the following baseline status categories:

- Normal/missing
- Abnormal according to PCSA criteria

For parameters for which no PCSA criteria are defined, similar table(s) using the normal range will be provided.

Drug-induced liver injury

The liver function tests, namely AST, ALT, alkaline phosphatase, and total bilirubin, are used to assess possible drug-induced liver toxicity.

The following analyses will be performed:

- Time to onset of the initial ALT or AST elevation ($>3 \times \text{ULN}$) and total bilirubin elevation ($>2 \times \text{ULN}$), whichever comes first will be analyzed using Kaplan Meier estimates by study cohort and treatment arm, if necessary.
- A graph of distribution of peak values of ALT versus peak values of total bilirubin (in logarithmic scale or in the scale of $x \text{ ULN}$ if appropriate) will also be presented. The graph will be divided into 4 quadrants with a vertical line corresponding to $3 \times \text{ULN}$ for ALT and a horizontal line corresponding to $2 \times \text{ULN}$ for total bilirubin if necessary. A similar graph will be provided for peak values of AST versus peak values of total bilirubin.
- Listing of possible Hy's law cases identified by treatment group (eg, patients with any elevated ALT or AST $>3 \times \text{ULN}$, and associated with an increase in bilirubin $>2 \times \text{ULN}$) with ALT, AST, alkaline phosphatase and total bilirubin values if necessary.
- Summary of the incidence of liver-related adverse events by treatment group if necessary. The selection of preferred terms will be based on the hepatic disorder SMQ.

